ACL injury is a common and potentially devastating injury. Approximately 80,000 ACL tears occur annually in the United States (1). 50,000 of those will go on to have ACL reconstruction surgery (2). Goals of reconstruction surgery and rehabilitation include: joint stability, restoration of knee function, and return to preinjury activities. The quadriceps is critical to dynamic joint stability, and weakness of this muscle group is related to poor functional outcomes. Because of this, identifying strategies to minimize quadriceps weakness following ACL injury and reconstruction is of great clinical interest (3). Moderated blood flow training, was developed in 1966 by [name] of Japan. This training technique uses specialized pneumatic belts, placed on the upper arms or legs that moderate blood flow to the distal extremity leading to engorgement of blood in the arms and legs. This exercise method has been shown to be safe and effective in producing muscle hypertrophy at lower intensity training (4,5). Typically a training intensity of more than 65% of one repetition maximum (1 RM) is considered the minimum intensity required to achieve muscle hypertrophy and strength gains (6). However, such intensive weight may not be possible or safe in the postoperative patient population. With moderated blood flow training, substantial muscle hypertrophy can occur using a training intensity as low as 20% of 1 RM (6). Moderated blood flow training provides a safe, less intense, but still effective means to promote muscle hypertrophy in the post-operative ACL patient. We hypothesize that patients randomized to standard physical therapy with moderated blood flow training will demonstrate significantly increased muscle strength, muscle mass, HGH, IGF levels, and no significant differences in knee range of motion, Lachman exam, KT2000, VAS scores, and CK levels compared with standard physical therapy without moderated blood flow in post-

operative ACL patients. This in turn could lead to faster, yet safer, return to functional day-to-day activities and sport.

Objectives: To determine if there are significant differences in muscle strength, thigh circumference, knee range of motion, VAS, IKDC, Tegner, PROMIS surveys, HGH, IGF, CK levels, KT2000, and Lachman’s exam in those patients that participate in moderated blood flow postoperative ACL physical therapy vs. standard ACL post-operative physical therapy.

Study Procedures

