- a. The study will be a prospective, randomized, controlled trial between two treatment cohorts. A total of 50 patients will be enrolled in the study. Informed consent will be obtained in clinic or by phone (Patient IQ e-consent) prior to any surgical intervention, per the IRB protocol. Enrollees will receive a copy of the consent and HIPAA form. All patients that meet inclusion criteria who consent to participate in the study will then be randomly assigned to either the control group or moderated blood flow therapy group. Randomization will occur by autogenerated permuted 1:1 block randomization using electronic assignment from the orthopaedic research team prior to initiation of post-operative therapy. The control group will undergo standard of care, post-operative ACL reconstruction rehabilitation. The treatment group will also receive standard ACL rehabilitation combined with Delfi moderated blood flow restriction therapy. Patients will follow up at standard of care clinic visits and participate in the same standard of care physical therapy protocol for ACL reconstruction. Baseline measurements of thigh circumference, knee ROM, KT 2000, Lachman exam, and labs for HGH, IGF, and CK will be obtained preoperatively. Patients will also complete preoperative IKDC, Tegner, PROMIS, and VAS pain surveys. Measurements of thigh circumference and knee range of motion will occur at 2 week intervals post operatively. Strength testing will start at 6 weeks post-operatively. These measurements will occur during standard therapy sessions. KT 2000 and Lachman exam will be performed at 4, 6, 8, and 12 months post operatively. A standard functional return to sport evaluation will be performed at the 4, 6, 8, and 12 month postoperative visits. Labs for HGH, IGF, and CK will be drawn at 2, 6, 12, and 24 weeks. VAS pain scores will be recorded before and after each therapy session. The PROMIS, IKDC, and Tegner surveys will be given at 4, 6, 8, 12 month intervals. The study will conclude at 12 month follow up. All post-operative visits will be standard of care. No additional clinic visits will be required for this study. Background patient information will be collected including age, sex, BMI, and co-morbidities.
- b. The control group will be necessary to provide a baseline measure on which moderated blood flow therapy will be compared.

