Withdrawal of Subjects: Subjects will be informed that they have the right to withdraw from the study at any time for any reason, without prejudice to their medical care. The Investigator(s) may elect at any time to withdraw a subject from the study for any reason unrelated to the study if such a decision is in the subject's best medical interest. If a subject discontinues the study prematurely, or is withdrawn by the Investigator(s), as much follow-up data as possible will be obtained. The primary reason for termination or discontinuation will be documented in the report of the final results. Subjects who are withdrawn for any reason from the study after treatment will not be replaced. Subjects who withdraw consent and refuse to complete the follow-up assessment will be considered off-study at that time. Attempts will be made to retrieve any follow-up data, in particular, adverse events at the time of study discontinuation. If the Investigator(s) reports a subject as lost to follow-up, an assistant to the Investigator will ensure that documentation is complete regarding the reason(s) this has occurred and will ensure that every attempt is made by the Investigator(s) to contact the subject or significant other persons associated with the subject to determine subject status. Appropriate documentation will consist of at least two documented attempts at contact via telephone by an assistant of the Investigator (s), followed by an attempt to contact via registered US mail or other courier service requiring recipient signature.

1. Inclusion/Exclusion Criteria

Inclusion Criteria:

-Patients between ages 18-40

-Diagnosed with isolated ACL tear and have been indicated to undergo ACL reconstruction

Exclusion Criteria:

- age <18 years old or >40 years old
- Multiligament knee injury
- Revision ACL reconstruction
- History or peripheral vascular disease
- History of deep vein thrombosis or pulmonary embolism
- Any contraindication to moderated blood flow restriction therapy
- Inability to comply with post-operative ACL reconstruction rehabilitation
- If meniscal repair or a cartilage procedure is performed at the time of surgery that would preclude the patient from being able to follow the standard post-operative ACL rehabilitation.

2. Devices

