Delfi's PTS Personalized Tourniquet System (Delfi Medical Innovations Inc., Vancouver, Canada), a form of moderated blood flow training, has been used by the Missouri Orthopaedic Institute Department of Physical Therapy for its proven safety and effectiveness in help to promote muscular strength gains, enhance sports performance, and to assist with rehabilitation from injury or surgery.

Moderated blood flow training causes increased blood pooling in the limbs. During exercise lactic acid is then produced. Due to the moderation of blood flow, the lactic acid is retained longer in the muscles. Hypoxia, acidosis, inorganic phosphate, AMP and other local factors have been shown to turn on transcription, and thus, protein synthesis in muscle cells. This local effect results in stimulation of muscle, tendon and vascular growth (5). Muscle receptors also send stronger signals to the brain which in turn causes large quantities of growth hormone to be released. Under the condition of moderated blood flow therapy, it has been shown that even short-term and low-intensity exercise can induce muscle strength, hypertrophy and increasing muscle mass (7-9).

3. Study Statistics

- a. Primary outcome variable will be muscle strength determined by a trained observer blinded to therapy cohort and time point.
- b. Secondary outcome variables will include: thigh circumference, VAS pain scores, IKDC, Tegner, PROMIS surveys, knee range of motion, KT 2000, Lachman exam, lab levels of HGH, IGF, and CK.
- c. Number of patients per group (n=25) was determined from a pre-study power analysis (t-Test) using previously published data on rehabilitation after ACL reconstruction for a desired power of 0.8 and alpha = 0.05. This analysis resulted in recommended sample size of 20 per group. The N of 25 per group was chosen to allow for subjects lost to follow-up.

4. Risks

- a. Patient confidentiality during the course of this study will be protected in compliance with HIPAA requirements as well as the requirements of the University of Missouri Health-Sciences IRB.

After consent is obtained, all subjects will be assigned a study identification number that requires the use of a key in order to decipher a subject's personal identification information. The key will be kept in the Cerner Power Trials database, which is password protected. The study identification number will be used to label all paper data collection instruments.

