All subject information in electronic format will be kept in password-protected storage. All subject information in paper format will be kept in locked cabinets in a secured suite at the Missouri Orthopedic Institute or destroyed.

b. There is potential risk of discomfort from application of the pneumatic tourniquets. This is temporary and occurs during the therapy sessions.

c. Due to the venous pooling from vascular constriction, there is a theoretical risk of increased incidence of blood clots, vascular insufficiency, potential muscle injury, oxidative stress, and possible nerve conduction problems. These theoretical risks have not been demonstrated in previous studies specifically investigating the safety of occlusive therapy (10,11).

5. Benefits

a. There is a potential benefit to the moderated blood flow group of increased muscle mass, strength, and ability to progress in therapy at an accelerated rate compared with control patients. If this benefit is found in the treatment group, moderated blood flow therapy may be able to be used in all ACL reconstruction patients. The hope is that the increased strength and muscle mass will allow patients to progress in therapy at a safe and accelerated rate, and therefore allow patients to get back to their preinjury activities. Otherwise, there are no further direct benefits to the patient for participation in the study.

6. Payment and Remuneration

a. No compensation for participation in the study.

7. Costs

a. Patients that choose to participate in the study will not incur any additional costs related to the study. Patients will receive the standard of care surgical procedure and postoperative rehabilitation protocols. Any additional lab tests and study related measurements will be at no charge to the patient and will be covered by the Department of Orthopaedic Surgery.

8. References

(1)Griffin, Letha Y., et al. "Noncontact anterior cruciate ligament injuries: risk factors and prevention strategies." *Journal of the American Academy of Orthopaedic Surgeons* 8.3 (2000): 141-150.

(2) Iwasa, J., Y. Shima, and L. Engebretsen. "Results of ACL reconstruction." *The Knee Joint*. Springer Paris, 2012. 245-262.

(3) Palmieri-Smith, Riann M., Abbey C. Thomas, and Edward M. Wojtys. "Maximizing quadriceps strength after ACL reconstruction." *Clinics in sports medicine* 27.3 (2008): 405-424.

(4) KAATSU-In Layman's Terms. <http://www.kaatsu-global.com/kaatsu-in-laymans-terms/> Accessed 11/9/15.

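### Clot, vascular and nerve events are named as cuff risks, but the plan describes no collection of them in patients who stay in the trial

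*Combined protocol and SAP*

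**What the plan says.** **Named harms.** Section 4 (Risks), item c states that "there is a theoretical risk of increased incidence of blood clots, vascular insufficiency, potential muscle injury, oxidative stress, and possible nerve conduction problems". It adds that the safety studies it cites have not shown these. Item b adds: "There is potential risk of discomfort from application of the pneumatic tourniquets", which it describes as temporary and confined to sessions. The exclusion criteria remove patients with earlier venous thrombosis, pulmonary embolism or peripheral vascular disease.

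**Adverse events.** The term occurs once, under Withdrawal of Subjects: "Attempts will be made to retrieve any follow-up data, in particular, adverse events at the time of study discontinuation". The sentence before it is about patients who withdraw consent and refuse follow-up.

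**What is measured.** Section 3 (Study Statistics), item b lists as secondary outcomes "thigh circumference, VAS pain scores, IKDC, Tegner, PROMIS surveys, knee range of motion, KT 2000, Lachman exam, lab levels of HGH, IGF, and CK". Under Study Procedures, item a, "Labs for HGH, IGF, and CK will be drawn at 2, 6, 12, and 24 weeks" and "VAS pain scores will be recorded before and after each therapy session". KT 2000 and Lachman are scheduled at 4, 6, 8 and 12 months. A footnote to the schedule table makes some of these later assessments, including the 8-month visit, depend on whether they are received as standard care.

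**What is hoped for.** The Background says: "This in turn could lead to faster, yet safer, return to functional day-to-day activities and sport". Section 5 (Benefits) hopes for safe, faster progress and foresees possible use in every ACL reconstruction patient if benefit is found.

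**The concern.** The plan identifies specific harms of the device, and the schedule starts therapy, with or without the cuff, on the first day after surgery. It then gives those harms no route into the dataset for a patient who completes the trial. An event that nobody asks about during follow-up cannot be recovered at analysis.

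At stake is the half of the benefit-risk question that the protocol itself raises. A strength gain would be reported beside a hope of safe progress and wider use, with no by-arm count of the events that bear on that hope. An absence of reported clots or nerve problems would then be uninterpretable, because it could mean either that none occurred or that none were recorded.

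**Working it through.** **Step 1. Each named harm set against the planned measurements**

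| Harm (section 4, b and c) | Planned measurement in both arms |
|---|---|
| Blood clots | None in the schedule or outcome list |
| Vascular insufficiency | None |
| Nerve conduction problems | None |
| Muscle injury | CK at baseline and weeks 2, 6, 12 and 24; indirect, since the plan does not call CK a muscle-injury marker and does not time draws relative to sessions |
| Oxidative stress | None |
| Cuff discomfort | VAS before and after sessions; indirect, since the discomfort is said to occur during them |

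KT 2000 and Lachman add joint laxity, which section 4 does not name as a cuff risk. The gap is therefore clots, vascular insufficiency and nerve problems, which a simple enquiry could cover, and oxidative stress, which it could not.

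**Step 2. The plan's own figure**

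The plan states 20 per group from a t-test power analysis (power 0.8, alpha 0.05), raised to 25 for loss to follow-up. The 20 cannot be reproduced forward because no effect size or SD is given. Solved backwards with a two-sided t-test, it implies a standardised difference of about 0.91. The trial was sized for a large strength effect, not for harms. Only the denominators 25 and 20 are used below.

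**Step 3. What full collection could show in one arm**

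With true event rate p, the chance of no events in n patients is (1 − p)^n. Setting this to 0.05 (one-sided 95%) or 0.025 (upper end of a two-sided 95% interval) gives the upper limit:

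- n = 25: 1 − 0.05^(1/25) = 11.3%; 1 − 0.025^(1/25) = 13.7%.
- n = 20: 1 − 0.05^(1/20) = 13.9%; 1 − 0.025^(1/20) = 16.8%.

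The chance of seeing at least one event among 25 is 1 − (1 − p)^25. The plan gives no event rates, so p is assumed over a range:

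| Assumed p | Chance of at least one event in 25 |
|---|---|
| 1% | 22% |
| 2% | 40% |
| 5% | 72% |
| 10% | 93% |

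**Step 4. What a between-arm test could show**

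With 25 per arm and no events in one arm, Fisher's exact test first falls below 0.05 at 6 versus 0 (p = 0.022). With 20 per arm it does so at 5 versus 0 (p = 0.047). With 25 per arm, its power is about 2% for assumed rates of 2% versus 10%, and about 20% for 5% versus 20%. A formal comparison would therefore be of little use. Counts with exact limits are the right form of report.

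**The case against.** The other side has several fair points.

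- **Some harm-related measures are compared.** A reader might infer that no harm at all can be compared between arms. That goes too far: CK, VAS pain and joint laxity are secondary outcomes in both arms, and the stated hypothesis expects no significant difference in them. None of them detects a clot, vascular insufficiency or a nerve problem.
- **Silence is not a rule.** A reader might infer that the withdrawal sentence limits adverse-event collection to patients who leave. It does not say so. It describes extra retrieval for leavers, and the plan says nothing about those who stay. Reporting arrangements may exist outside this document, but none is described that would seek events the same way in both arms.
- **Share of events missed.** It is tempting to use the gap between 20 and 25 per group to estimate what fraction of events would be captured. The documents do not support this. No loss rate is stated, loss to follow-up is not the same as discontinuation, and an event may itself be a reason to stop.
- **Uneven detection.** A reader might suppose that cuff patients are watched more closely. No section says so, and surgeons and the evaluators of strength, circumference, motion, Lachman and KT 2000 are blinded. Patients are not blinded, so uneven reporting is possible, but it is not documented.
- **No safety claim is made.** The Background says only that a safer return could follow, section 4 calls the risks theoretical, and no safety hypothesis is stated. This stands. It limits the point to what the trial could support, and does not accuse the plan of claiming safety.
- **The trial is too small.** This also stands, as Steps 3 and 4 show. It argues against a formal test and for cautious wording, but not against asking.

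**Conclusion.** The point holds in a limited form. For clots, vascular insufficiency and nerve problems, all named by the protocol as cuff risks, no prospective collection is described in patients who remain in the trial, so these harms cannot be compared by arm. Muscle injury and discomfort are covered indirectly. The primary strength analysis is untouched. The plan should be changed because the omission cannot be repaired after follow-up and is cheap to prevent.

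Even complete collection has a limited reach. Zero events would leave rates of 11.3% to 13.7% not excluded with 25 patients, and 13.9% to 16.8% with 20, according to whether the 95% limit is one- or two-sided. These limits assume independent patients and that every event is found. The trial could describe these harms but could not establish safety for rare ones.

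**What to change.** - **Outcome.** Add a secondary safety outcome to section 3, item b: clot (deep vein thrombosis or pulmonary embolism), vascular events, nerve events and any other adverse event.
- **Ascertainment.** Use the same short checklist in both arms at therapy sessions, where VAS is already recorded, and at clinic visits already attended, through 12 months. Add it to the schedule table. Record that it was asked, so that no event can be told apart from no enquiry.
- **Reporting.** For each event type separately, give the number of patients with an event by randomised arm, with exact confidence limits. Do not pool the types. List cuff discomfort for the cuff arm only, since controls cannot have it, and leave out oxidative stress, which a checklist cannot detect. CK, VAS and laxity stay as planned.
- **Interpretation.** State in advance that the table is descriptive, give the zero-event limits for the number actually followed, and say that it cannot establish safety for rare events.

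**Cost.** One short form at existing contacts and one extra table, with no added visit or change in sample size. The form adds a small burden, and answers come from unblinded patients, so differences in reporting between arms remain possible and should be acknowledged. Any statement on safe progress would have to be more modest.

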*Moderated Blood Flow Restriction after Anterior
Cruciate Ligament Reconstruction*

Identifiers: NCT02911909

Unique Protocol ID: 2004255

Date: 06-14-2019

Date: 06-14-2019
Version Number: 3.1
Principal Investigator: [name], DVM, PhD, OTSC
Application Number: 2004255
Application Title: Moderated blood flow restriction after anterior cruciate ligament reconstruction

Moderated Blood Flow Restriction after Anterior Cruciate Ligament Reconstruction

Principal Investigator: [name], DVM, PhD, OTSC
Department of Orthopaedics
[name]
Email: [contact]
[contact]

Coordinating Site: University of Missouri, Missouri Orthopaedic Institute

Funding: Department of Orthopaedic Surgery, University of Missouri

Hypothesis- Patients in the moderated blood flow (Delfi) restriction group will have significantly increased muscle strength, thigh circumference, HGH and IGF levels, and no significant differences in knee range of motion, Lachman exam, KT2000, IKDC, Tegner, PROMIS surveys, VAS scores, or CK levels compared with standard ACL rehabilitation patients.

Background:

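### A non-significant comparison of CK between arms cannot support a conclusion that the cuff causes no muscle injury; a by-arm table of individual CK elevations is needed

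*Combined protocol and SAP*

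**What the plan says.** The document is a combined protocol and SAP, and four places bear on this point.

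- **Risk.** Section 4, item c, attributes to the cuff a theoretical risk of clots, vascular insufficiency, "potential muscle injury, oxidative stress, and possible nerve conduction problems". The next sentence says that studies of the safety of occlusive therapy have not shown these effects.
- **Measurement.** Study Procedures, item a, has a preoperative baseline and then: "Labs for HGH, IGF, and CK will be drawn at 2, 6, 12, and 24 weeks". The Hypothesis expects HGH and IGF to rise with treatment, which leaves CK as the only one of the three that speaks to muscle injury.
- **Criterion.** The Hypothesis predicts "no significant differences in knee range of motion, Lachman exam, KT2000, IKDC, Tegner, PROMIS surveys, VAS scores, or CK levels" relative to standard rehabilitation. The Background repeats this for CK, and the Objectives ask whether the arms differ significantly.
- **Analysis.** Section 3, item b, places "lab levels of HGH, IGF, and CK" among the secondary outcomes. The only test named anywhere is in item c, where the sample size "was determined from a pre-study power analysis (t-Test) using previously published data on rehabilitation after ACL reconstruction". No test is named for CK.

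The plan contains no count or listing of individual CK values and no by-arm safety table. Adverse events are mentioned once, under Withdrawal of Subjects, as something to retrieve at discontinuation.

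**The concern.** Muscle injury happens to individual patients, whereas a comparison of CK levels between arms asks whether the two groups differ as groups. A large rise in one patient raises that arm's mean and its standard error together, so the test statistic does not grow with the size of the rise.

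At stake is how the CK result can be read. The predicted finding, no significant difference, is what the comparison would usually return even with a gross elevation in the cuff arm. A reader who set that finding beside the risk section could take it as reassurance about muscle injury. Section 5, item a, raises the possibility of using the therapy in all ACL reconstruction patients if benefit is found, so the reading could matter beyond this trial.

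**Working it through.** **Inputs from the document.** Allocation is 1:1. Section 3, item c, plans "for a desired power of 0.8 and alpha = 0.05" and states "This analysis resulted in recommended sample size of 20 per group", with 25 per group enrolled to allow for loss.

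**The plan's own figure.** No effect size or SD is given, so 20 can only be inverted. At 80% power and two-sided alpha 0.05 (sidedness is not stated) it implies a standardized difference of about 0.91; one-sided, about 0.80. The step to 25 matches 20% loss: 20/(1 − 0.20) = 25. These figures neither confirm nor refute 20; they fix the range of n used below, 20 to 25 per arm.

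**Algebra, with no assumption about the CK distribution.** Let k patients in one arm of n share a very large value M, with all other values negligible beside it.

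- Difference in means: kM/n.
- Variance in that arm: M²k(n − k)/[n(n − 1)].
- Standard error of the difference, equal arms: (M/n)·√[k(n − k)/(n − 1)].
- Ratio: t = √[k(n − 1)/(n − k)].

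M cancels. For k = 1, t = √[(n − 1)/(n − 1)] = 1 at any n. For k = 4 and n = 20, t = √(4 × 19/16) = 2.18.

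| Extreme cases in cuff arm, none in control | n = 20: t, p | n = 25: t, p |
|---|---|---|
| 1 | 1.00, 0.324 | 1.00, 0.322 |
| 2 | 1.45, 0.154 | 1.45, 0.155 |
| 3 | 1.83, 0.075 | 1.81, 0.077 |
| 4 | 2.18, 0.036 | 2.14, 0.038 |

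Four such cases are needed for p < 0.05. With arms otherwise identical and one value raised without limit, Welch's test gives p = 0.33 and Mann-Whitney 0.81 to 0.82. If the extreme value replaces the lowest one in its arm, t peaks at about 1.06 for n = 20, against a critical value of about 2.02. The limit of 1 also holds for change from baseline or a per-patient average over the draws, because one patient still supplies the one extreme number. A repeated-measures model was not checked.

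**Simulation, with an assumed CK distribution.** CK is taken as lognormal with median 150 U/L and log-SD 0.6, the same in both arms, with one cuff patient set to the value shown. There were 10,000 runs per setting. Entries are the percentage of runs with p < 0.05, for n = 20 / n = 25.

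| Value set (U/L) | t, raw scale | t, log scale | Mann-Whitney |
|---|---|---|---|
| none | 4.7 / 5.2 | 5.1 / 5.3 | 5.0 / 4.9 |
| 1,000 | 3.3 / 3.6 | 5.3 / 4.9 | 5.3 / 4.6 |
| 2,000 | 0.2 / 0.4 | 4.5 / 4.5 | 4.3 / 4.5 |
| 5,000 | 0 / 0 | 4.0 / 4.2 | 4.7 / 4.5 |
| 10,000 | 0 / 0 | 3.3 / 3.8 | 4.9 / 4.7 |
| 50,000 | 0 / 0 | 2.0 / 2.4 | 5.2 / 4.6 |

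Simulation error near 5% is about √(0.05 × 0.95/10,000) = 0.2 percentage points. With log-SD 0.5 (4,000 runs), the raw-scale t-test was significant in 0.15%, 0% and 0% of runs at 2,000, 10,000 and 50,000 U/L for n = 25, and in 0.05%, 0% and 0% for n = 20.

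**What a count can and cannot show.** Fisher's exact test for 4 against 0 gives p = 0.106 (n = 20) and 0.110 (n = 25), so a count is not a sharper test. Seeing no case among n patients leaves a one-sided 95% upper limit of 1 − 0.05^(1/n): 13.9% at n = 20 and 11.3% at n = 25. The table would be descriptive.

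**The case against.** The best reply is that the plan never calls CK a safety or muscle-injury marker and never says that muscle injury will be judged by comparing CK. It also names no test for CK, calls the risk theoretical, and reports it as not demonstrated. That a single outlier pulls t towards 1 is true of any two-sample comparison of means, and nothing here shows that such a case is likely. All of this stands, and it limits the point to what a non-significant CK result can support.

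Four stronger readings are tempting, and the documents do not carry them.

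- A reader might infer that the plan intends to declare the cuff safe on CK. It states no such conclusion.
- A reader might infer that one extreme case makes significance impossible. The result is only that one case does not produce it by its own force. If the arms differ by chance or through treatment, a rank or log-scale test can still be significant.
- A reader might infer that abnormal results would go unread until the final analysis. The plan is silent on how results are handled, and silence does not show that.
- A reader might equate a gross CK value with a serious clinical event. CK alone does not establish severity.

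It is also fair to say that the wider gap is in adverse-event collection and reporting. A CK table would not cover clots, vascular insufficiency or nerve problems. That does not make the arm comparison adequate for muscle injury.

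**Conclusion.** The point holds in this limited form. The only stated criterion for CK is a difference between arms. With 20 to 25 per arm, that criterion is close to blind to one gross elevation: t tends to 1 and p to about 0.32. Up to three such cases in the cuff arm against none in control would leave a t-test on means non-significant if the arms were otherwise alike. Even without an outlier, non-significance would not show that the arms are the same, because no equivalence margin is set. A non-significant CK comparison therefore cannot support a conclusion that the cuff causes no muscle injury.

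The t = 1 limit depends on no CK distribution. The log-scale and rank results rest on the assumed lognormal CK, two-sided alpha 0.05 and arms that are otherwise alike. The primary outcome, muscle strength, is unaffected.

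**What to change.** Keep the arm comparison of CK as a secondary outcome, name its method, and state that a non-significant result will not be read as evidence of no muscle injury. Add one descriptive by-arm table from the values already drawn:

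- each patient's maximum post-operative CK;
- a listing of values above the laboratory's reference range;
- the number of patients per arm above a multiple of the upper limit that the investigators fix in advance.

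The counts should be given with their denominators and without a claim of safety if they are zero, since the upper limit would still be 11% to 14%.

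The cost is one extra table and no extra blood draws. The downside is that CK rises due to exercise or surgery may need explaining; showing the control arm and the preoperative baseline alongside helps with that. Any clinical review of, or action on, individual results is for the investigators to decide.
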